### Source of Materials

Upon patient's consent, relevant clinical and demographical data will be collected. Specifically, obstetrical history, course of the previous current pregnancy(s), history of prior surgery and a connective tissue disorders (i.e. Ehlers-Danlos Syndrome, Benign Joint Hypermobility Disorder, etc.), race, age, height, weight, and parity will be documented.

Prior to taking the CM scan, standard obstetric external and internal vaginal examination will be performed by a clinical investigator. Attention to cervix softness, elasticity and any abnormalities

will be made and the results recorded to map the cervix surface. A 4-point grading system for cervix elasticity would be giving soft (0), or moderately soft (1), or moderately stiff (2), or stiff (3) elasticity scores to cervix. These subjective measurements would then be correlated with the CM data for agreement or discordance.

The CM examination will be performed as described above in Methods and Procedures section. The process is quick, non-invasive and should cause no additional discomfort to the patient as compared to a standard pelvic examination. All results will be recorded using an examination chart, which will be a part of the Case Report Form (CRF) specifically designed for the study. The chart will summarize all findings by all mean to characterize the cervix in terms of appearance and elasticity.

All necessary clinical and demographic data will be derived from existing records and de-identified. No additional clinical tests will be ordered to support this research. A specific clinical study number will be generated for each examination case so the link between the data and the patient will be created without revealing patient identity.

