### Subjects

The study will involve 10 non-pregnant, 2 CM measurements per subject. Adult non-pregnant pre-menopausal women scheduled for a regular gynecological examination at Princeton Urogynecology (Princeton, NJ) will be considered eligible for enrollment into the study. Each patient will first be studied with the existing clinical means and then with the CM. A clinical research assistant will maintain a log as to any concerns/complications with the CM.

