## Enrollment

Conditions precluding patients from participation are listed in the study exclusion criteria below. In addition, cognitively impaired patients will not be asked to participate. No patients will be excluded on the basis of race. Adult women in reproductive age (21-44 years) will be included.

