### Inclusion criteria

1. Adult women age 21-44 years
2. Non-pregnant women

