## **Protection of Human Subjects**

### Human Subjects Involvement, Characteristics and Design

Adult non-pregnant women scheduled for a regular gynecological examination at Princeton Urogynecology (Princeton, NJ) will be considered eligible for enrollment into the study with Cervix Monitor (CM). Conditions precluding patients from participation are listed in the study exclusion criteria below. This study with non-pregnant women is conducted to assess potential risks to pregnant women and fetuses as required by Code of Federal Regulations, Title 45, §46.204(a). This study with non-pregnant women will be conducted before initiation the study with pregnant women.

The highest priority will be given to consideration of examination safety with CM probe, disturbing the cervix tissue during pregnancy and potential risk of premature delivery, infection or miscarriage. Clinical study coordinators will maintain a log as to any concerns, complications, or suggested improvements in using the CM probe. After the CM examination a questionnaire will be presented to patients to assess their comfort and pain concerns relative to the procedure. All clinical investigators will have their CV on file with the local IRB and complete training and certification in Protecting Human Research Participant. Explanation of how data from the sites will be obtained, managed, and protected is presented in Data and Safety Monitoring Plan section (see below).

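### Does the plan need to state how and when non-pregnancy is confirmed before the Cervix Monitor examination?

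*Combined protocol and SAP*

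**What the plan says.** Inclusion criteria has two items, an age range and "Non-pregnant women". Enrollment adds that "Adult women in reproductive age (21-44 years) will be included", and Subjects describes the population as "Adult non-pregnant pre-menopausal women scheduled for a regular gynecological examination". Exclusion criteria rules out women whose uterus has been removed and contains no item on pregnancy, contraception or sterility.

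Human Subjects Involvement, Characteristics and Design explains why the status matters: "This study with non-pregnant women will be conducted before initiation the study with pregnant women". Recruitment and Informed Consent repeats that order.

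On checking eligibility, Recruitment and Informed Consent requires assessment against the inclusion criteria before enrollment, usually at the initial clinical screening. The admission process comprises forms, consent, and a history and physical examination.

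On the order of events, Subjects says "Each patient will first be studied with the existing clinical means and then with the CM". Source of Materials says "Prior to taking the CM scan, standard obstetric external and internal vaginal examination will be performed by a clinical investigator", and also asks for obstetric history once consent is given. In its last paragraph, after a statement that clinical and demographic data come from existing records, it adds "No additional clinical tests will be ordered to support this research".

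**The concern.** The participants are of reproductive age and must have a uterus, so early unrecognised pregnancy is possible. Yet no section says how non-pregnancy is established or how recent the check must be. A literal reader of the sentence on additional tests could conclude that the site may not order a test for this purpose.

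At stake is the sequence on which the study rests. A woman with an unrecognised pregnancy could be examined with the probe before the risk assessment that is meant to come first. The protocol itself names miscarriage among its safety concerns, and it has the consent form describe risk to the fetus as not yet foreseeable.

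Two features sharpen the point. Protection Against Risks lists mitigations for tissue damage, infection, toxicity, malfunction, electrical shock and confidentiality, but none for inadvertent exposure of a pregnancy. The obstetric history in Source of Materials is taken after consent, whereas the consent interview follows the finding that the woman is acceptable. That particular history is therefore not tied to the eligibility decision.

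**Working it through.** No formula applies and the plan gives no figure to reproduce. The check is a reading of the sections side by side.

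1. **Is the omission real?** Yes. Six sections refer to non-pregnant participants: Study Objectives, Subjects, Inclusion criteria, Human Subjects Involvement, Recruitment and Informed Consent, and Importance of the Knowledge to be Gained. None of the six, nor Enrollment, nor Source of Materials, states a confirmation method (0) or a maximum interval to the CM examination (0).

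2. **Is there a check at all?** Yes. Assessment against the inclusion criteria before enrollment is mandatory for every patient, and non-pregnancy is one of those criteria. Study admission has its own history and physical examination, separate from the history in Source of Materials. The timing of the latter therefore does not leave eligibility unsupported, and nothing in the plan prevents a later finding from leading to exclusion.

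3. **Is this criterion treated differently from the others?** No. There are 2 inclusion and 13 exclusion criteria, 2 + 13 = 15 in all, and none states a verification procedure. The HIV and hepatitis B item is worded in terms of serology without saying whether it is tested or read from records. The item on cardiac conditions only assigns the judgement to the attending physician. The plan leaves verification to the site throughout.

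4. **Does the sentence on tests bar a pregnancy test?** Its neighbours are a sentence on deriving data from existing records and one on study numbers that protect identity. The subject is where data come from. A strictly literal reading of that paragraph already fails within the protocol: the same section has an investigator examine the cervix and record a new score from 0 to 3, and Data Collection includes a new patient questionnaire. The wording is loose and is not a screening rule. Even read literally, it would not exclude a result obtained in routine care.

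5. **Is there an interval to limit?** Women come for a scheduled gynecological examination, the CM follows the existing clinical means, and a vaginal examination precedes the scan. Consent takes place in the pre-procedure facility. No section describes a separate later CM visit. The qualifier that screening is usually done at the initial evaluation leaves room for a gap, but none is planned.

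6. **Does anything downstream change?** No. The end points are safety, comfort and capability; ICC of at least 0.90 with limits of agreement within ±15% for elasticity; and ICC of at least 0.93 with limits within ±10% for length. None of these definitions, nor the Bland-Altman and ICC analysis, depends on how non-pregnancy is established.

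**The case for a change.** The strongest case for a change is that the required safeguards are generic. The history and physical examination are not described as directed at pregnancy. The examination before the scan is directed at cervical softness, elasticity and abnormalities. The order in which women are studied is presented as a regulatory commitment, and the expectation of no added risk is a prediction that this study exists to test. On that view, one sentence and a qualifier would cost almost nothing and would remove any doubt about whether a test is allowed.

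The factual part of this stands: the method is unstated, and the sentence on tests could be more tightly worded. The rest carries less weight. A sentence requiring confirmation, with method and timing left to the investigator and the IRB, would largely restate the pre-enrollment assessment already required and would supply no better method. The two statements do not contradict each other, so there is nothing to reconcile. The case report form and the admission forms are not among the documents, and the consent pages were removed. A specific screening item may exist there, and its absence from the available text cannot be counted against the plan.

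**Conclusion.** No change to the plan follows. The plan requires non-pregnancy and requires that it be assessed before enrollment; what it omits is the operational detail of that assessment. Clinicians at a gynecology site, screening women of reproductive age for a study defined by their not being pregnant, can be expected to fill that gap sensibly. The sentence on additional tests is best read as describing data sources, and the interval concern is hypothetical because no later CM visit is scheduled.

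The point covers one criterion in 10 women and leaves every endpoint and analysis as it is. Its clinical probability cannot be sized, because the documents contain no rate of unrecognised pregnancy. The conclusion rests on two assumptions: that the pre-enrollment assessment is carried out as written, and that the site reads the sentence on tests in its context.

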#### Potential Risks

Investigators do not expect any additional risks or side effects from the use of CM beyond those normally associated with standard manual palpation and transvaginal ultrasound, such as extremely rare possibility of physical damage of the vagina, cervix tissue and infection. Other risks include software/hardware malfunction, toxicity, allergic reaction, electrical shock and breach of confidentiality.

#### Recruitment and Informed Consent

Patients scheduled for vaginal examination will undergo a standard study admission protocol. This includes: completion of administrative and clinical forms, procedure informed consent, and a history and physical examination. Prior to enrollment, each patient will be assessed against the study inclusion criteria, usually during their initial clinical screening evaluation. Once a patient has been found to be acceptable for participation in the study, the consent interview will be conducted in private in the pre-procedure facility by the clinical research coordinator or clinical investigator performing the procedure. All informed consents will be reviewed and approved by the institution IRB prior to the initiation of the study. Subjects will be informed of the potential risks and benefits of the research and of their right to withdraw from the study at any time without penalty. A statement that the particular CM examination procedure may involve risks to the subject and to the fetus which are currently unforeseeable will be included into the informed consent as required by Code of Federal Regulations (CFR) Title 45, §46.116(b)(1). The subject will be free to ask any questions pertaining to the study. Informed consents will be signed and dated by the subject, investigator and research assistant.

According to the requirements of CFR Title 45, §46.204 (a), the study with pregnant women will follow after assessment of the risks of CM examination procedure with non-pregnant.

We will comply with all applied requirements of CFR Title 45, Part 46, Protection of Human Subjects, in Subpart B – Additional Protections for Pregnant Women, Human Fetuses and Neonates Involved in Research.

#### Protection Against Risks

All investigators performing the CM examination will receive appropriate training in order to negate the lack of familiarity with the device. The risk of physical damage to the vagina and cervix will be minimized by utilization of standard procedure to assess the cervix using a speculum. A physical contact of the probe tip with the cervix surface will be detectable by a tactful feedback from the CM probe. The risk of cross-contamination and infection will be

eliminated by the use of disposable (single use) probe shaft which be sterilized and stored in a sterile sheath before the clinical use. It is highly unlikely that the use of the CM probe can produce any toxicity since the probe shaft is made of certified biocompatible.

Software and hardware malfunction risks are minimized by completion of full component and system testing cycle prior to the initiation of the clinical study. The devices will go through performance bench testing on simulator models to verify proper CM functionality. Standard software verification and validation procedures mitigate the risk of incorrect characterization being presented to the user during the patient examination. All participating clinical investigators will be trained to recognize inappropriate software and hardware behavior and to react on it.

Possible risks to the patient caused by electrical shock are negligible due to absence of supplied voltage to the probe, to protective features of electronics and isolated medical-grade power supply to electronics and computer. The device will go through a full cycle of EMC and electrical safety testing at an independent certified test facility. If ordered by local IRB, the device will be also tested by appropriate hospital personnel responsible for biomedical safety.

To protect against the risk of breach of confidentiality, patient confidentiality will be maintained at all times. The record of patient's progress while on this study will be kept in locked file cabinets to which only limited research staff will have access. The confidentiality of any central computer record will be carefully guarded, and no information by which patient can be identified will be released or published. All information on the case report forms or any information communicated from clinics to the company will be de-identified. The psychological risk will be minimized by the fact that no change in clinical diagnosis and patient management will result from this study.

We will complete full Risk Analysis for CM, as required by our internal Quality Management System under ISO 13485, according to American National Standard ANSI/AAMI/ISO 14971: Medical Devices – Application of Risk Management to Medical Devices.

#### Potential Benefits of the Proposed Research to Human Subjects and Others

There are no direct benefits to the patients in the study. However, there may be a benefit to society, in general, from the knowledge gained in connection with participation in the study.

#### Importance of the Knowledge to be Gained

The proposed clinical studies in the first exploratory stage of the project will allow to assess potential risks of CM to pregnant women in studies with non-pregnant women, to develop and test the data collection technique and establish possible limitations in the CM use, to assess CM measurement reproducibility, evaluate the probe ergonomic design and ease of use, and to assess the clinical suitability of the interface software to facilitate the data collection process and to get *in vivo* test data for off-line development of analysis routines. After meeting the basic research milestones in the exploratory stage, we plan extensive clinical studies on pregnant patients to obtain quantitative data on changes of cervix elasticity for the months of pregnancy, on estimating the level of the cervix softening which may qualify the patient for a medical treatment and on the range of variability of cervix stiffness which need to be taken into account while making decisions on clinical intervention.

#### Data and Safety Monitoring Plan

The Principal Investigator will be responsible for proper monitoring of the investigation and compliance with written monitoring procedures (§§ 812.46 and 812.25(e)); ensure that IRB approval is obtained (§812.42) and any reviewing IRB and FDA are promptly informed of significant new information about an investigation (§812.150); control distribution and disposition of investigational products (§812.43).

Clinical investigators perform the data safety monitoring function and are responsible for concurrent reporting of any adverse events that occur as a result of this study to the local approving IRB and to the Principal Investigator. All events will be categorized as to their degree of seriousness and relation to the use of the PTI. Principal Investigator will collect and analyze adverse effects, highlight its course and propose means to negate such effects.

ATI staff will monitor the study by auditing CRFs, verifying the consistency of raw CM data, and checking clinical protocol compliance. Communication with clinical investigators will be primarily in a form of phone and e-mail. In addition, ATI's representative will visit all participating clinical sites. Establishment Inspection Report (EIR), a detailed record of the inspection and findings, will be prepared after the visit. Also, such interactions will result in a clinical database that will be set to store all information obtained during the course of the study.

To protect patient data, confidentiality will be maintained at all times. All records will be identified by a study specific code and personal identifiers and linkage to study identification numbers will be maintained separately in locked file cabinets to which only designated research staff will have access. Each patient will be identified with a unique patient identification number (xxxxxxxxxxxx) that consists of the patient number (001xxxxxx) and the date (xxx020102) in day-month-year format. Data for that study are all placed in a study specific patient folder. A file that matches patient identifier to a patient name and hospital ID number are kept on a password protected computer. No individual subject will be identified by name in any reports from the study. Patient's records, with regard to participation in this study, may be subject to review by the appropriate officers of the hospital conducting the clinical study and its Institutional Review Board, and patient's insurance carrier. In addition, the National Institutes of Health and Food and Drug Administration (FDA) may request and will be given access to records of participants in this study. This clinical study will be registered in ClinicalTrials.gov as required by Public Law 110-85, Title VIII and Certification of Compliance under 42 U.S.C. § 282(j).

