## Device

Cervix Monitor (CM)

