#### Inclusion of Children

Participating gynecology departments serve only adult patients; therefore our cross section of the population will not include individuals under 21 years of age. Additionally, children are not likely to benefit from the LTI technology, given no available supporting evidence of incidence of pelvic organ prolapse in children.

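### Adverse events need reporting only if the examining investigators attribute them to the study, and relatedness is then graded against an undefined term, PTI, instead of the CM

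*Combined protocol and SAP*

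**What the plan says.** All references are to the combined protocol and SAP.

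- **Who monitors.** Data and Safety Monitoring Plan: "Clinical investigators perform the data safety monitoring function". Protection Against Risks: "All investigators performing the CM examination will receive appropriate training". Recruitment and Informed Consent also describes a clinical investigator as the person performing the procedure. The examiners are therefore also the safety reporters.
- **What they report.** They are "responsible for concurrent reporting of any adverse events that occur as a result of this study to the local approving IRB", and also to the Principal Investigator.
- **How events are graded.** The next sentence reads: "All events will be categorized as to their degree of seriousness and relation to the use of the PTI". PTI appears nowhere else. The Device section names only the Cervix Monitor (CM).
- **Other safety records.** Subjects: "A clinical research assistant will maintain a log as to any concerns/complications with the CM". Human Subjects Involvement, Characteristics and Design gives a similar log, kept by study coordinators and worded around use of the CM probe. It adds a patient questionnaire on comfort and pain after the examination, which Data Collection also lists.
- **What safety is for.** Assessing risk is the first Study Objective, and a safe examination is part of end point 1 under Study End Points. The study in pregnant women is to follow this assessment.

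**The concern.** The reporting duty contains a causal test. An event must first be thought to result from the study, and the relatedness grading comes after that. An investigator who believes an event has another cause has no stated duty to report it, so it need not be graded or seen by anyone else.

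Attribution is hard in this setting. The women are already scheduled for a regular gynecological examination (Subjects), and an internal vaginal examination precedes the CM scan (Source of Materials). Potential Risks expects nothing beyond the risks of manual palpation and transvaginal ultrasound. Discomfort, tissue injury or infection therefore has a ready explanation other than the CM examination. Whether the CM adds risk is what the study is meant to find out, so the reporting rule should not depend on a prior answer.

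What is at stake is the completeness of the safety record that is to precede the study in pregnant women. With so few subjects, each missing event counts.

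**Working it through.** The plan states no event rate, confidence bound or precision target for safety, so there is no figure to reproduce. The check is mainly of the text.

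**1. Scope against grading.** Reporting covers events resulting from the study; grading covers all events. If all events means all reported events, those judged to have another cause are never graded. If it means every event that occurs, the grading sentence needs input that the reporting sentence does not secure. Either way the two sentences must be reconciled.

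**2. What falls outside the duty.** Attribution to the study is broader than attribution to the device. The speculum is the first step of the examination under Methods and Procedures, so an event blamed on it is reportable. The exposed events are those put down to routine gynecological care or to something outside the study. The internal examination before the scan is a borderline case: it is a standard examination, but its findings are recorded and scored for this study.

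**3. Other channels.** The logs and questionnaire are not the investigators' event reports, so they can capture some of what those reports miss. Three limits remain:
- Both logs are worded around the CM or its probe, so they carry an attribution limit of their own.
- The questionnaire asks about comfort and pain. No later contact is stated, although infection is a listed risk and would appear after the visit.
- No section sends log or questionnaire entries to adverse-event review, or says which sources decide the safety part of end point 1.

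**4. PTI.** The same section refers to "verifying the consistency of raw CM data". Inclusion of Children contains a second undefined label, in a sentence about prolapse: "children are not likely to benefit from the LTI technology". Together these suggest text carried over from another project.

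**5. Scale, under assumptions.** The one input from the documents is n = 10 (Sample Size). The true event rate p and the share of events reported s are assumed. Each woman has at most one event, and events and reporting are independent. Then

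P(at least one event reported) = 1 − (1 − p·s)^10.

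| True rate p | s = 100% | s = 75% | s = 50% | s = 25% |
|---|---|---|---|---|
| 5% | 40% | 32% | 22% | 12% |
| 10% | 65% | 54% | 40% | 22% |
| 20% | 89% | 80% | 65% | 40% |

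For example, p = 10% and s = 50% give 1 − 0.95^10 = 0.401.

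If no event is reported among 10 women, the one-sided 95% upper bound on the reported rate is 1 − 0.05^(1/10) = 25.9%. Dividing by s gives the bound on the true rate: 25.9/0.75 = 34.5% and 25.9/0.50 = 51.8%. At s = 25% the quotient exceeds 100%, so there is no useful bound.

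**The case against.** The strongest reply is that the plan does not depend on investigator reports alone. Staff keep logs of any concerns or complications, and patients are asked directly about pain and comfort. The Principal Investigator collects and analyzes adverse effects, sponsor staff audit the case report forms, and a database is to hold all information obtained. Study-caused and device-related are also different questions, so grading after reporting is not circular: an event can result from the study and still be unrelated to the CM.

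Much of this stands. A reader might infer that the whole safety result is filtered by the examiner's opinion. The documents do not support that, because the filter applies to investigator reports and the other records exist. What survives is the missing link: those records are tied to the CM, and nothing says that they enter adverse-event review or end point 1. An audit or database can only show an event that someone had reason to record.

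A reader might also infer from PTI that safety is being assessed on the wrong device, or that every event would be graded as unrelated. That does not follow either. No section says that PTI is a device, and the objective, the end point, the logs and the questionnaire all refer to the CM or its examination. It is a drafting error, but it sits in the plan's only relatedness rule.

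**Conclusion.** The point holds in a limited form. Attribution to the study is a condition for reporting, and it is left to the investigators who perform the examination, before relatedness is graded. Events put down to routine care or outside causes can be lost to the Principal Investigator, and the other records offset this only in part. The relatedness sentence names an undefined label and needs correcting. This should be changed, because safety is the first objective and part of the first end point.

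The size is unknown. No figure in the documents is affected, and end point 1 defines no event count or threshold, so a reader cannot infer a demonstrated bias in a planned estimate. The probabilities and bounds above show only that, with 10 women, losing a quarter to a half of events would matter. They rest on assumed event rates and reporting shares.

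**What to change.** Replace the reporting and grading sentences in the Data and Safety Monitoring Plan with wording such as:

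> Clinical investigators record every adverse event from the start of the study visit to [stated end of collection], whatever its suspected cause, and send all of them to the Principal Investigator, including log and questionnaire entries that describe symptoms or injury. Concurrent reporting to the local IRB continues as at present. Each event is then graded for seriousness, for relation to the CM and, separately, for relation to the standard examination.

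This keeps the existing IRB reporting and replaces PTI with CM. The sponsor needs to state the end of the collection period, since none is given now.

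Under Study End Points, base the safety part of end point 1 on all recorded events and show the CM-related subset separately.

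The cost is protocol wording and a small change to the case report form. The downside is that a few more minor events will be recorded, and the safety summary may look somewhat less favourable.
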